**RO7049389—F. Hoffmann-La Roche Ltd**

51/Protocol YP39406, Version 4

Adverse Events [NCI CTCAE] criteria; see Section 5.2.3); the event itself may be of relatively minor medical significance (such as severe headache without any further findings).

Severity and seriousness need to be independently assessed for each adverse event recorded on the eCRF.

Serious adverse events are required to be reported by the Investigator to the Sponsor immediately (i.e., no more than 24 hours after learning of the event; see Section 5.3.2, for reporting instructions) and to the local health authority and IRB/EC, if required by local requirements.

### **5.1.3 Non-Serious Adverse Events of Special Interest (Immediately Reportable to the Sponsor)**

Non-serious adverse events of special interest are required to be reported by the Investigator to the Sponsor immediately (i.e., no more than 24 hours after learning of the event; see Section 5.3.2 for reporting instructions). Adverse events of special interest for this study include the following:

- Cases of an elevated ALT or AST in combination with either an elevated bilirubin or clinical jaundice, as defined in Section 5.2.5.6.
- Suspected transmission of an infectious agent by the study drug, as defined below:

Any organism, virus, or infectious particle (e.g., prion protein transmitting transmissible spongiform encephalopathy), pathogenic or non-pathogenic, is considered an infectious agent. A transmission of an infectious agent may be suspected from clinical symptoms or laboratory findings that indicate an infection in a Subject exposed to a medicinal product. This term applies only when a contamination of the study drug is suspected.

## **5.2 METHODS AND TIMING FOR CAPTURING AND ASSESSING SAFETY PARAMETERS**

The Investigator is responsible for ensuring that all adverse events (see Section 5.1.1 for definition) are recorded on the Adverse Event eCRF and reported to the Sponsor in accordance with instructions provided in this section and in Sections 5.3, 5.4, and 5.5.

For each adverse event recorded on the Adverse Event eCRF, the Investigator will make an assessment of seriousness (see Section 5.1.2 for seriousness criteria), severity (see Section 5.2.3), and causality (see Section 5.2.4).

### **5.2.1 Adverse Event Reporting Period**

Investigators will seek information on adverse events at each study subject contact. All adverse events, whether reported by the study subject or noted by study personnel, will be recorded in the study subject's medical record. Adverse events will then be reported on the Adverse Event eCRF as follows:

**After informed consent** has been obtained **but prior to initiation of study drug**, only serious adverse events caused by a protocol-mandated intervention should be reported (e.g., serious adverse events related to invasive procedures such as biopsies). Any other adverse event should not be reported.

**After initiation of study drug**, all adverse events, regardless of relationship to study drug, will be reported until **28 days** after the last dose of study drug.

**After a period of 28 days** from the last dose of study drug, investigators should report any deaths, serious adverse events, or other adverse events of concern that are believed to be related to prior treatment with study drug (see Section [5.5](#)).

### **5.2.2 Eliciting Adverse Event Information**

A consistent methodology of non-directive questioning should be adopted for eliciting adverse event information at all study subject evaluation time-points. Examples of non-directive questions include the following:

“How have you felt since your last clinic visit?”

“Have you had any new or changed health problems since you were last here?”

### **5.2.3 Assessment of Severity of Adverse Events**

[Table 2](#) provides guidance for assessing adverse event severity.

**Table 2 Adverse Event Severity Grading Scale**

Severity	Description
Mild	Discomfort noticed, but no disruption of normal daily activity
Moderate	Discomfort sufficient to reduce or affect normal daily activity
Severe	Incapacitating with inability to work or to perform normal daily activity

Note: Regardless of severity, some events may also meet seriousness criteria. Refer to definition of a serious adverse event (see Section [5.1.2](#)).

#### **5.2.4 Assessment of Causality of Adverse Events**

Investigators should use their knowledge of the study subject, the circumstances surrounding the event, and an evaluation of any potential alternative causes to determine whether or not an adverse event is considered to be related to the study drug, indicating "yes" or "no" accordingly. The following guidance should be taken into consideration:

- Temporal relationship of event onset to the initiation of study drug.
- Course of the event, considering especially the effects of dose reduction, discontinuation of study drug, or reintroduction of study drug.
- Known association of the event with the study drug or with similar treatments.
- Known association of the event with the disease under study.
- Presence of risk factors in the study subject or use of concomitant medications known to increase the occurrence of the event.
- Presence of non-treatment-related factors that are known to be associated with the occurrence of the event

#### **5.2.5 Procedures for Recording Adverse Events**

Investigators should use correct medical terminology/concepts when recording adverse events on the Adverse Event eCRF. Avoid colloquialisms and abbreviations.

Only one adverse event term should be recorded in the event field on the Adverse Event eCRF.

##### **5.2.5.1 Diagnosis versus Signs and Symptoms**

A diagnosis (if known) should be recorded on the Adverse Event eCRF rather than individual signs and symptoms (e.g., record only liver failure or hepatitis rather than jaundice, asterixis, and elevated transaminases). However, if a constellation of signs and/or symptoms cannot be medically characterized as a single diagnosis or syndrome at the time of reporting, each individual event should be recorded on the Adverse Event eCRF. If a diagnosis is subsequently established, all previously reported adverse events based on signs and symptoms should be nullified and replaced by one adverse event report based on the single diagnosis, with a starting date that corresponds to the starting date of the first symptom of the eventual diagnosis.

#### **5.2.5.2 Adverse Events Occurring Secondary to Other Events**

In general, adverse events occurring secondary to other events (e.g., cascade events or clinical sequelae) should be identified by their primary cause, with the exception of severe or serious secondary events. However, medically significant adverse events occurring secondary to an initiating event that are separated in time should be recorded as independent events on the Adverse Event eCRF. For example:

- If vomiting results in mild dehydration with no additional treatment in a healthy adult, only vomiting should be reported on the eCRF.
- If vomiting results in severe dehydration, both events should be reported separately on the eCRF.
- If a severe gastrointestinal hemorrhage leads to renal failure, both events should be reported separately on the eCRF.
- If dizziness leads to a fall and subsequent fracture, all three events should be reported separately on the eCRF.

All adverse events should be recorded separately on the Adverse Event eCRF if it is unclear as to whether the events are associated.

#### **5.2.5.3 Persistent or Recurrent Adverse Events**

A persistent adverse event is one that extends continuously, without resolution, between study subject evaluation time-points. Such events should only be recorded once on the Adverse Event eCRF. The initial severity of the event should be recorded, and the severity should be updated to reflect the most extreme severity any time the event worsens. If the event becomes serious, the Adverse Event eCRF should be updated to reflect this.

A recurrent adverse event is one that resolves between Subject evaluation time-points and subsequently recurs. Each recurrence of an adverse event should be recorded separately on the Adverse Event eCRF.

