##### 3.1.1 Overview of Study Design

This study will leverage the data which will have been generated in the FIH study, allowing targeted evaluation of fewer doses.

Healthy subjects will be enrolled into one of 3 planned cohorts and one optional cohort. Cohort 1 will include 4 healthy subjects, with 2 randomly assigned to RO7049389 and 2 assigned to placebo. From Cohort 2 to Cohort 4, each of the cohorts will include 12 healthy subjects with 10 subjects randomly assigned to RO7049389 and 2 subjects randomly assigned to placebo.

In Cohort 1, subjects will receive one single dose of the assigned study medication. In subsequent cohorts, subjects will receive one single dose of the assigned study medication, followed by a wash-out period of approximately 1-week before entering into a MAD phase of the study. Subjects in the MAD cohorts will be from the SAD cohorts after the wash-out period (see [Figure 1](#)), or from new enrollments if there are discontinuations between the SAD phase and MAD phase for reasons other than safety.

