### **3.1.1.2 MAD Phase**

In Cohorts 2, 3 and 4, after a post-SAD phase wash-out period of at least one week, all subjects will be admitted to a clinical research unit for 16 nights from Day -1 to Day 16 (discharged on Day 16). Subjects will be administered multiple oral doses of either RO7049389 or placebo twice daily (q12h) or once daily (q24h) from Day 1 to Day 14 (the currently planned regimen is q12h, but will be evaluated based on emerging data from Study YP39364). The allocation of RO7049389 or placebo will be the same as that which was administered in the SAD phase. All subjects will return for a follow-up visit on Day 21 ( $\pm 1$ ), and will receive a follow-up call on Day 42.

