#### **5.2.5.4 Abnormal Laboratory Values**

Not every laboratory abnormality qualifies as an adverse event. A laboratory test result should be reported as an adverse event if it meets any of the following criteria:

- Accompanied by clinical symptoms.
- Results in a change in study treatment (e.g., dosage modification, treatment interruption, or treatment discontinuation).
- Results in a medical intervention (e.g., potassium supplementation for hypokalemia) or a change in concomitant therapy.
- Clinically significant in the Investigator's judgment.

It is the Investigator's responsibility to review all laboratory findings. Medical and scientific judgment should be exercised in deciding whether an isolated laboratory abnormality should be classified as an adverse event.

If a clinically significant laboratory abnormality is a sign of a disease or syndrome (e.g., alkaline phosphatase and bilirubin 5 times the ULN associated with cholecystitis), only the diagnosis (i.e., cholecystitis) should be recorded on the Adverse Event eCRF.

If a clinically significant laboratory abnormality is not a sign of a disease or syndrome, the abnormality itself should be recorded on the Adverse Event eCRF, along with a descriptor indicating if the test result is above or below the normal range (e.g., "elevated potassium", as opposed to "abnormal potassium"). If the laboratory abnormality can be characterized by a precise clinical term per standard definitions, the clinical term should be recorded as the adverse event. For example, an elevated serum potassium level of 7.0 mEq/L should be recorded as "hyperkalemia".

Observations of the same clinically significant laboratory abnormality from visit to visit should not be repeatedly recorded on the Adverse Event eCRF, unless the etiology changes. The initial severity of the event should be recorded, and the severity or seriousness should be updated any time the event worsens.

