### **6.5.1 Adverse Events**

The original terms recorded on the eCRF by the Investigator for adverse events will be standardized by the Sponsor.

Adverse events will be summarized by MedDRA coded term. In addition, adverse events will be summarized by their toxicity level (according to the maximum reported severity level) and severity (severe vs. non-severe). All serious adverse events, including deaths, severe adverse events (Grade  $\geq 3$ ), and adverse events of special interest will be listed and summarized separately. Adverse events leading to study drug discontinuation or interruption will be summarized as well. Subjects will be tabulated by treatment (RO7049389 vs. pooled placebo group) and dose level.

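### An adverse event that starts after the single dose and worsens during 14-day dosing is one record at its worst severity with no rule assigning it to SAD or MAD, so at least one phase is misreported

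*Combined protocol and SAP*

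**What the plan says.** **Design.** Section 3.1.1 states: "Subjects in the MAD cohorts will be from the SAD cohorts after the wash-out period". The only exceptions are new enrolments replacing subjects who left for non-safety reasons. The single dose is "followed by a wash-out period of approximately 1-week before entering into a MAD phase of the study", and section 3.1.1.2 adds: "The allocation of RO7049389 or placebo will be the same as that which was administered in the SAD phase". In Table 1 the two phases of a cohort use different regimens: 400 mg then 200 mg q12h (Cohort 2, MAD optional), 600 mg then 400 mg q12h (Cohort 3), and 800 mg then 600 or 800 mg q24h (Cohort 4, optional).

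**Recording.** For an event that continues without resolution, section 5.2.5.3 says "Such events should only be recorded once on the Adverse Event eCRF" and "the severity should be updated to reflect the most extreme severity any time the event worsens". Section 5.2.5.4 says "Observations of the same clinically significant laboratory abnormality from visit to visit should not be repeatedly recorded on the Adverse Event eCRF"; that sentence goes on to make an exception when the etiology changes. Section 5.2.5.5 has the same rule and exception for vital signs. Section 5.2.5.3 has no such exception. Under section 5.2.1, reporting runs to 28 days after the last dose, so it covers washout and MAD without a break.

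**Analysis.** Section 6.5.1 summarises events by maximum reported severity and adds: "Subjects will be tabulated by treatment (RO7049389 vs. pooled placebo group) and dose level". It does not mention phase.

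**The concern.** The recording rule suits one continuous course of treatment. Here the same person is dosed again with another regimen while an earlier event may still be open. Once severity is overwritten, the record no longer shows how severe the event was before the first MAD dose, and the analysis section does not ask for that information.

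The primary objective covers safety after single and after multiple doses. A complaint that is tolerable after one dose and grows on repeat dosing is part of what the MAD phase should reveal. The tables serving the primary objective could put that growth in the wrong phase or leave it out, and nothing in the plan lets a reader of the tables tell which has happened.

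**Working it through.** **1. The plan's own figure.** Section 6.1 gives 10 active subjects per dose group, an incidence of 25% and a 94% chance of seeing at least one event:

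1 − (1 − 0.25)^10 = 1 − 0.0563 = 0.9437.

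The figure reproduces. For a MAD dose group, it describes the MAD row only if MAD events are counted there.

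**2. What happens to one spanning event.** Take a subject whose event is mild after the single dose, unresolved at the first MAD dose, and severe on MAD. A correct report is mild in SAD and severe in MAD. The plan yields one record, graded severe, and leaves its assignment open:

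| Assignment of the single record | SAD row | MAD row | Misreported |
|---|---|---|---|
| By onset | severe | nothing | both |
| To MAD | nothing | severe | SAD |
| To both phases | severe | severe | SAD |
| To the cohort as a whole | not separated | not separated | phases cannot be read |

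No choice in the table recovers both phases from one record at maximum severity. The defect therefore does not depend on which choice the programmer makes.

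**3. Whether dose level resolves it.** It does not. In Table 1, 200 mg is the Cohort 1 single dose and the Cohort 2 q12h dose; 400 mg is the Cohort 2 single dose and the Cohort 3 q12h dose. The 600 mg and 800 mg doses can also occur in both phases. A row labelled only by milligrams does not identify a phase.

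**4. Two counting rules in one row.** Section 5.2.5.8 makes a condition present at screening an adverse event if it worsens during the study. A replacement subject who enters directly into MAD with a mild condition that worsens therefore contributes a MAD event. Under section 5.2.5.3, a continuing subject with a mild open event and the same course gets no new record.

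**5. Size per subject.** 1/10 = 10 percentage points of incidence, at a given severity, in each misreported row.

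**6. Illustration only.** The documents do not say what share f of MAD events would be worsenings of an open SAD event. Suppose such events were all booked to SAD. The chance of at least one event in a MAD row of 10, at a true incidence of 25%, becomes 1 − (1 − 0.25 × (1 − f))^10:

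| Assumed f | Incidence left in the MAD row | Chance of at least one |
|---|---|---|
| 0 | 25% | 94.4% |
| 10% | 22.5% | 92.2% |
| 20% | 20% | 89.3% |
| 30% | 17.5% | 85.4% |
| 50% | 12.5% | 73.7% |

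These values of f are assumptions that show a range. They do not estimate bias in this trial.

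**The case against.** **The stronger reading.** A reader might infer that a MAD effect is definitely counted at the SAD dose. The documents do not say so. Section 5.2.5.3 does not state which onset date the updated record keeps. The nearest rule, in 5.2.5.1, keeps an early date ("with a starting date that corresponds to the starting date of the first symptom of the eventual diagnosis"), but only where a diagnosis replaces symptoms. Section 6.5.1 does not assign events by onset. Booking to SAD is one of several possible outcomes.

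**Escalation.** A reader might also infer that the counts in the dose-escalation stopping rule would shift. The text does not support this. Escalation rests primarily on safety to 48 hours after the single dose (3.1.2). Individual data are reviewed before each step (4.2.1), an unblinded sponsor review is added, and escalation can be halted for other findings whatever their incidence (3.1.2.1). These reviewers do not depend on the final 6.5.1 tables.

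**Laboratory and ECG findings.** A rising transaminase looks like the natural example, but it is largely covered elsewhere. Laboratory values and changes from baseline are summarised by visit (6.5.2), marked abnormalities are flagged (6.5.2.2), and ECG intervals are summarised by nominal time (6.5.4). An investigator could also use the etiology exception in 5.2.5.4 and 5.2.5.5 to open a new record, although it is unclear whether redosing with the same drug qualifies.

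**Narrow pathway.** The event must last through washout, and an event that resolves and recurs already gets its own record. MAD entry needs agreement between sponsor and investigator, and a limited re-screening. Section 5.1.1 counts worsening of a known condition as an adverse event, which could support a new record.

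**Recoverability.** Initial severity is entered before it is updated, and the audit trail in 7.2 dates each change.

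Most of this stands and limits the scope. It does not remove the point. The audit trail and the initial entry do not feed the adverse event tables, and 5.2.5.3, which governs symptomatic events, has no exception. Whether the case report form captures a date of worsening cannot be judged from these documents.

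**Conclusion.** The point holds within limits. For an event that begins after the single dose, is unresolved at the first MAD dose and worsens on MAD, the one-record rule combined with tabulation at maximum severity misreports at least one phase, whichever assignment is used. The direction of the error is not fixed by the plan.

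The size is 10 percentage points per affected subject in a row of 10 active subjects. The number of such subjects is unknown and may be zero. The active-versus-placebo split is unaffected, because allocation carries over between phases. The problem is confined mainly to symptomatic events that outlast the washout.

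The conclusion assumes that 5.2.5.3 is applied as written and that no separate data-handling document already sets a phase rule. It is a modest defect, worth correcting because it bears on the primary objective and is cheap to remove in advance.

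**What to change.** **Sections 5.2.5.3 to 5.2.5.5.** State that the first MAD dose is a new baseline for recording adverse events. If an event open at that point worsens later, capture the date and severity of the worsening, either as a new adverse event record linked to the earlier one or as a dated severity change on the same record. The dated change avoids giving a continuous event an artificial end date. An event that continues without worsening stays as a single SAD record.

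**Section 6.5.1.** State that:
- adverse events are summarised separately for SAD and MAD;
- the SAD row uses the maximum severity reached before the first MAD dose;
- worsening after that dose counts in the MAD row, at the MAD regimen.

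**Cost.** A few sentences, an update to the form completion guidance, and a few extra records or fields. One continuous event may appear in both phase tables, so a footnote should say so and any overall count should be by subject.

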#### **5.2.5.4 Abnormal Laboratory Values**

Not every laboratory abnormality qualifies as an adverse event. A laboratory test result should be reported as an adverse event if it meets any of the following criteria:

- Accompanied by clinical symptoms.
- Results in a change in study treatment (e.g., dosage modification, treatment interruption, or treatment discontinuation).
- Results in a medical intervention (e.g., potassium supplementation for hypokalemia) or a change in concomitant therapy.
- Clinically significant in the Investigator's judgment.

It is the Investigator's responsibility to review all laboratory findings. Medical and scientific judgment should be exercised in deciding whether an isolated laboratory abnormality should be classified as an adverse event.

If a clinically significant laboratory abnormality is a sign of a disease or syndrome (e.g., alkaline phosphatase and bilirubin 5 times the ULN associated with cholecystitis), only the diagnosis (i.e., cholecystitis) should be recorded on the Adverse Event eCRF.

If a clinically significant laboratory abnormality is not a sign of a disease or syndrome, the abnormality itself should be recorded on the Adverse Event eCRF, along with a descriptor indicating if the test result is above or below the normal range (e.g., "elevated potassium", as opposed to "abnormal potassium"). If the laboratory abnormality can be characterized by a precise clinical term per standard definitions, the clinical term should be recorded as the adverse event. For example, an elevated serum potassium level of 7.0 mEq/L should be recorded as "hyperkalemia".

Observations of the same clinically significant laboratory abnormality from visit to visit should not be repeatedly recorded on the Adverse Event eCRF, unless the etiology changes. The initial severity of the event should be recorded, and the severity or seriousness should be updated any time the event worsens.

#### **5.2.5.5 Abnormal Vital Sign Values**

Not every vital sign abnormality qualifies as an adverse event. A vital sign result should be reported as an adverse event if it meets any of the following criteria:

- Accompanied by clinical symptoms.
- Results in a change in study treatment (e.g., dosage modification, treatment interruption, or treatment discontinuation).
- Results in a medical intervention or a change in concomitant therapy.
- Clinically significant in the Investigator's judgment.

It is the Investigator's responsibility to review all vital sign findings. Medical and scientific judgment should be exercised in deciding whether an isolated vital sign abnormality should be classified as an adverse event.

If a clinically significant vital sign abnormality is a sign of a disease or syndrome (e.g., high blood pressure), only the diagnosis (i.e., hypertension) should be recorded on the Adverse Event eCRF.

Observations of the same clinically significant vital sign abnormality from visit to visit should not be repeatedly recorded on the Adverse Event eCRF, unless the etiology changes. The initial severity of the event should be recorded, and the severity or seriousness should be updated any time the event worsens.

